2 STUDY DESIGN

This is a phase 2 multi-center, randomized, double blind, placebo-controlled, parallel group study in patients with mild to moderate Alzheimer's disease.

[figure not shown]
Participants will be randomized to one of two groups: 280 mg of BHV-4157 or placebo. The BHV-4157 treatment dose of 280 mg was selected for evaluation in the current study based on evidence summarized in Section 1.8. Double-blind treatment duration is approximately 48 weeks (12 months). There is a screening period of up to 42 days and a 4-week post-treatment observation period (for subjects who do not participate in the Open-Label Extension phase).

In addition, subjects who are completing or have completed the Double-blind treatment phase may be offered the opportunity to enroll in an Open-Label Extension phase, in which subjects will receive open-label treatment with BHV-4157 for approximately 48 weeks. Enrollment into the Open-Label Extension phase for all subjects is contingent on the PI's judgement that open-label treatment offers an acceptable risk-benefit profile for each individual. All subjects who enter the Open-Label Extension phase will need to sign a new informed consent form.

- Participants who are completing the double-blind treatment phase may directly enter the Open-Label Extension phase. These participants should not complete the follow-up safety visit at Week 52 (of the double-blind treatment phase). Instead, these participants should continue directly into the Open-Label Extension phase starting at Week 48 (of the double-blind treatment phase). The Week 48 visit will serve as the Baseline visit in the Open-Label Extension phase for participants who are going directly from the double-blind treatment phase to the OLE. Thereafter, participants will undergo visits at Week 4, Week 8, Week 12, and then every 12 weeks of the Open-Label Extension phase as outlined in Table 3 (Schedule of Assessments/Time & Events- Extension Phase).
- Participants who previously completed the double-blind treatment phase prior to the Open-Label Extension phase of the study being open for recruitment at their study center, may also enter the Open-Label Extension phase.

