8.1.9 Week 48 or Early Termination (± 7 days)

Every effort should be made to conduct the Week 48 visit and maintain the +/- 7 day window. However, due to concerns related to the COVID-19 pandemic, the Week 48 visit window may be modified beyond the +/- 7 day window, in order to minimize any potential risks to study participant safety and to comply with governmental and local institutional guidance (e.g., study site has a policy that a clinical research visit must be delayed). Under these circumstances, the visit window may be extended (up to a maximum treatment duration of 60 weeks), but every attempt should be made to conduct the visit as close to the date the visit is due as possible. If the visit window is modified, participants should be evaluated remotely (e.g., via phone) at the time of the scheduled Week 48 visit to perform and document appropriate safety assessments. Study medication may be sent to the participant via tracked courier. For any such cases, the investigator should discuss the specific circumstances of each case with the sponsor medical monitor (or designee) who must approve the request prior to any modification of the visit window.

Sponsor Medical Monitor

All participants returning for week 48 will undergo the following procedures:

- Physical exam
- Vital signs (sitting blood pressure, pulse, temperature, respiration rate)
- Weight
- Documentation of concomitant treatment
- Documentation of adverse events
- Blood samples for:
 - Safety laboratory tests (hematology and serum chemistry, as listed in Section 8.2)
 - Pharmacokinetics* (in plasma)
 - Biomarker/banking
- Urinalysis (see Section 8.2)
- Resting 12-lead ECG
- Lumbar puncture* (± 14 days of week 48)
- Post lumbar puncture safety telephone follow-up (1 to 3 days after lumbar puncture)
- Sheehan Suicidality Tracking Scale
- ADAS-Cog 11
- CDR-SOB
- Volumetric MRI (± 14 days of week 48)
- NPI
- ADCS-ADL
- Neuropsychological Test Battery
 - Craft Story 21 (Immediate and Delayed)
 - Benson Complex Figure
 - Multilingual Naming Test (MINT)
 - Letter & Category Fluency
 - Trail Making Test A&B
 - Number Span Test
- MMSE
- Montreal Cognitive Assessment (MoCA)
- Research Satisfaction Survey

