8.1.12 Open-Label Extension Phase (as applicable)

The Extension Phase is an optional open-label 48-week treatment phase. The investigator will be responsible for evaluating any major changes in the participant's status to determine their participation in the open-label extension. This should be based on the status of the participant at the end of the double-blind phase, the participant's risk-benefit profile as determined by the site PI, the consent of the participant, and the integrity of the trial.

If the participant has completed the double blind treatment phase prior to the Open-Label Extension Phase being approved at their study center, they can re-consent and start the study as long as the investigator determines that open-label treatment offers an acceptable risk-benefit profile for the individual. Once the study site is open for recruitment for the Open-Label extension, participants that completed the study prior will have up to 12 weeks to enroll in the Open-Label study.

When sites have opened for recruitment for the Open-Label Extension Phase, participants completing the double-blind treatment phase must go directly from the Week 48 visit into the Extension Phase if they choose and are eligible to continue.

 Participants who are completing the double-blind treatment phase may directly enter the Open-Label Extension phase. These participants should not complete the follow-up safety visit at Week 52 (of the double-blind treatment phase). Instead, these participants should continue directly into the Open-Label Extension phase starting at Week 48 (of the double-blind treatment phase). The Week 48 visit will also serve as the Baseline visit in the Extension Phase for participants who are going directly from the double-blind treatment phase to the OLE. Thereafter, participants will undergo visits at Week 4, Week 8, Week 12, and then every 12 weeks of the Extension Phase as outlined in Table 3 (Schedule of Assessments/Time & Events- Extension Phase).

- Participants who previously completed the double-blind treatment phase prior to the Open-Label Extension phase of the study being open for recruitment at their study center, may also enter the Open-Label Extension (OLE) phase.

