 - Week 24 and week 48 vMRI: the protocol window for vMRI at week 24 and week 48 is 14 days before and up to 14 days after the clinic visit. If participant is terminating early at 36 week or after, obtain vMRI if MRI is performed on the same day as a lumbar puncture at week 48, the vMRI must be conducted before the lumbar puncture. Otherwise, at least a 3-day window between vMRI and the lumbar puncture is required.
- 12 It is anticipated that lumbar puncture will be performed on an estimated 100 study participants as part of a sub-study (separate informed consent required).
- Only for the CSF sub-study. Visit windows for CSF are: up to 14 days prior to first dose of study medication and up to 14 days prior to weeks 24 and 48. If a participant in the CSF sub-study is terminating early, they do not need to undergo lumbar puncture.
- Post lumbar puncture safety follow up telephone call must occur 1 to 3 days after the lumbar puncture is performed.
- First dose of study medication will be given in the clinic at the baseline clinic visit after completion of the baseline visit procedures.
- Participants will receive a phone call during Week 2 from site study personnel in order to assess study drug tolerability. If tolerable, then the participant will be instructed to proceed with dose escalation.
- 17 Treatment blinding questionnaire to be administered to site PI and Raters.

Table 3: Schedule of Assessments and Events – Open-Label Extension Phase

Visit Number	1	2	3	4	5	6	7	8	9	10	
Study Visit Timepoint	Baselinel	Abbrev- iated Drug Dispensat ion Visit ²	Ext Week 2 (+/- 7 days)	Ext Week 4 (+/- 7 days)	Ext Week 8 ³ (+/- 7 days)	Ext Week 12 (+/- 7 days)	Ext Week 24 (+/- 7 days)	Ext Week 36 (+/- 7 days)	Ext Week 48 or Early Term (+/- 7 days)	Week2 Post last dose (+/- 7 days)	Unsched- uled Visit ⁴ (+/- 7 days)
Informed Consent	X	X									
Medical History	X										
Adverse Event Assessment	X	X	X	X	X^3	X	X	X	X	X	X
Telephone Check-in ⁵ Includes AE assessment and concomitant medication review			X		X ³						
Laboratory Assessments ⁶	X			X	X^3	X	X	X	X		
Urinalysis	X						X		X		
Physical Exam	X								X		
Physical Measurement - Weight	X						X		X		
Vital Signs	X	X		X		X	X	X	X	X	X
12-Lead ECG	X					X	X		X		
Concomitant Medication Review	X	X	X	X	X	X	X	X	X	X	X
Sheehan Suicidality Tracking Scale (S-STS)	X	X		X		X	X	X	X	X	
Dispense Study Drug	X	X		X		X	X	X			
Volumetric MRI ⁷	X								X		
ADAS-Cog 11	X						X		X		
CDR-SOB	X						X		X		

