- 6. Clinical Safety Laboratory Tests will be performed by a Central Laboratory. Assessment includes the following: Hematology (hemoglobin, hematocrit, platelets, RBC, WBC, differential count, and absolute neutrophil count), Chemistry (sodium, potassium, chloride, calcium, ALT, AST, LDH, alkaline phosphatase, GGT, phosphorus, bicarbonate, CPK, total protein, albumin, indirect bilirubin, direct bilirubin, total bilirubin, glucose, creatinine, BUN, uric acid, folate).
- 7. Volumetric MRI is not required if the participant's Double-Blind Week 48 MRI scan occurred less than than 3 months prior to their joining the Open-Label Extension Phase.

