# Table 4:Analysis Windows for All efficacy assessments and the VolumetricMRI, in the 48 week Extension Phase

Evaluation	Protocol-Specified Day	Analysis-Specified Interval
Extension Phase		
Week 24	Day 168	Day 2-252
Week 48	Day 336	Day 253-420

Note: Baseline assessment will be defined as the last available assessment on or before first day of extension phase study drug as long as it is within 28 days of the first day of extension phase medication. Days based on days from first day of extension phase study drug.

Table 5:	Analysis Windows for Safety Parameters: Sheehan Suicidal
	Tracking, Vital Signs, Lab Assessments, and ECG in the 48 week
	Extension Phase

Evaluation	Protocol-Specified Day	Analysis-Specified Interval
Extension Phase		
Week 4	Day 28	Day 2-42
Week 8	Day 56	Day 43-70
Week 12	Day 84	Day 71-126
Week 24	Day 168	Day 127-210
Week 36	Day 252	Day 211-294
Week 48	Day 336	Day 295-420

Note: Baseline assessment will be defined as the last available assessment on or before first day of extension phase study drug as long as it is within 28 days of the first day of extension phase medication. Days based on days from first day of extension phase study drug.

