#### 4.5.2 Primary Analysis After Double-blind Randomization Phase and Final Analysis After OL Extension Phase

The primary efficacy (including the primary, secondary and exploratory endpoints of the Randomization Phase) and safety analysis will be conducted after the last subject completes their Week 48 visit, or discontinues from the Randomization Phase. The study will be unblinded and the primary analyses will include all data from the double-blind Randomization Phase of the study, but will not include summaries of efficacy and safety data accumulated from the Extension Phase.

Interim looks at data from the Extension Phase may be performed after the completion and unblinding of the Randomization Phase, particularly for safety purposes.

A final analysis of the Open Label Extension Phase data will be completed after the last subject completes their last study visit. This will summarize for descriptive purposes all efficacy data collected in the open-label Extension Phase as well as all safety, laboratory, and other data collect though the entire study. Change from baseline will be based on the Extension Phase Baseline, unless otherwise specified.

Additional analyses may be conducted during the open label Extension Phase of the study to support regulatory and administrative requirements.

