#### 4.8 Efficacy Evaluation

Unless otherwise noted, all efficacy analyses will be conducted using all available in-clinic assessments from the mITT population during the double blind phase. Remote assessments during the double blind phase will be included in sensitivity analyses. All efficacy data will be included in listings by participant, treatment group, visit and phase (as applicable).

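### For participants who roll over directly, the Week 48 MRI window runs past the first open-label dose, and no rule requires the scan to come first

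*Protocol*

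**What the plan says.** **Scan timing.** The Week 48 procedure list in Protocol 8.1.9 has "Volumetric MRI (± 14 days of week 48" days. Table 1 footnote 11 (Appendix I) is fuller: "the protocol window for vMRI at week 24 and week 48 is 14 days before and up to 14 days after the clinic visit". Neither place makes an exception for participants entering the extension.

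**Rollover.** Protocol 8.1.12 says of sites already open for the extension that "participants completing the double-blind treatment phase must go directly from the Week 48 visit into the Extension Phase", if they choose to continue and are eligible. Section 2 likewise says these participants "should continue directly into the Open-Label Extension phase starting at Week 48". For them the Week 48 visit doubles as the extension baseline. The only ordering rule is that this visit be held in person before enrolment; it does not mention the scan. Table 3 marks an MRI at extension baseline, and footnote 7 waives it if the "Double-Blind Week 48 MRI scan occurred less than than 3 months prior to their joining the Open-Label Extension Phase". Footnote 1 requires a separate extension baseline visit only after a dosing break of 4 weeks or more.

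**Analysis.** SAP 4.4 ends the on-treatment efficacy period of the randomized phase no later than the first open-label dosing day, and counts later efficacy assessments as extension data. SAP 4.5.2 says the primary analyses cover the double-blind phase "but will not include summaries of efficacy and safety data accumulated from the Extension Phase". SAP 4.8 bases efficacy on "all available in-clinic assessments from the mITT population during the double blind phase". SAP 4.8.4.1 restricts the main hippocampal ANCOVA to participants with a scan in the Week 48 analysis window, which Table 2 sets at Day 253-420.

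**The concern.** The scan window and the rollover rule were written separately and overlap. A site can scan a direct rollover ten days after the Week 48 visit, comply fully, and obtain an image taken after open-label dosing has begun. The SAP does not say in one place what to do with that image. Either it leaves the main ANCOVA, or it is counted in a double-blind comparison although the participant has had open-label drug.

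Bilateral hippocampal volume is one of four secondary endpoints tested by Holm's procedure, and is formally tested only if both co-primaries are significant. Because the main ANCOVA needs a scan in the Week 48 window, losing that scan removes the participant from it. The Week 24 scan can then serve only the exploratory last-scan ANCOVA or the later repeated-measures analysis. What is at stake is avoidable loss of precision and an open question about which scans count.

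**Working it through.** The plan states no sample size or power for hippocampal volume, so there is no figure to reproduce. The check is day arithmetic, followed by an illustration of cost.

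**Day arithmetic.** Inputs: Week 48 is Day 336; the scan may be up to 14 days after the visit; the Week 48 MRI window is Day 253-420 (SAP Table 2). Assumption: the first open-label dose falls on the day of the Week 48 visit, as direct entry implies.

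1. With the visit and first open-label dose on Day 336, a compliant late scan falls on Day 337 to 336 + 14 = 350.
2. Counted from the first open-label dose as extension Day 1, that is extension Day 2 to 15. Under SAP 4.4 it belongs to the extension, and SAP 4.5.2 and 4.8 then keep it out of the double-blind analyses.
3. By Table 2 alone, Day 337-350 lies inside Day 253-420. SAP 4.3.8 adds that analysis windows are continuous so that all data are included. A programmer using only the day count would keep the scan, with up to about 14 days of open-label drug behind it.
4. The Week 24 scan cannot take its place. Its latest compliant day is 168 + 7 + 14 = 189, before Day 253.
5. A visit delayed by COVID-19 to the 60-week limit is on Day 420. A scan up to 14 days later reaches Day 434, which is outside Table 2 as well.

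A scan on or before the first open-label dosing day is not affected.

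**Illustrative cost if late scans are excluded.** Inputs: 248 participants with Week 48 data (336 x 0.74, the plan's dropout allowance) and an assumed 80% power at two-sided 5%. Let f be the fraction of Week 48 scans lost.

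- Scans lost = 248 x f
- Increase in standard error = 1/sqrt(1 - f) - 1
- Power = Phi((1.960 + 0.842) x sqrt(1 - f) - 1.960)

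The fraction f is the share of scans from direct rollovers times the share of those done late. Both shares are assumptions.

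| Direct rollovers x late | f | Scans lost | SE increase | Power |
|---|---|---|---|---|
| 0.25 x 0.05 | 1.25% | 3.1 | 0.6% | 79.5% |
| 0.50 x 0.10 | 5% | 12.4 | 2.6% | 78.0% |
| 0.75 x 0.20 | 15% | 37.2 | 8.5% | 73.3% |

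For the middle row, 2.802 x sqrt(0.95) - 1.960 = 0.771, and Phi(0.771) = 0.780.

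**The case against.** The best reply is that the plan already expects the scan first. Protocol 8.7 and Table 3 call for an extension-baseline MRI, and footnote 7 waives it only for a Week 48 scan that preceded joining. A direct rollover with an outstanding scan does not meet the waiver, so a baseline scan is still owed. This shows the intention, and it stands as such. But footnote 1 removes the separate visit at which that scan would be done, the 14 days after the visit remain available to everyone, and no text ties the scan to the first dose.

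A second reply is that exclusion is inferred. SAP 4.4 defines on-treatment periods rather than eligibility for the ANCOVA, and Table 2 read by day count keeps the scan. That is fair: exclusion is the better-supported reading, not an explicit rule. The uncertainty is itself a reason for one clarifying sentence.

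A reader might also infer a serious loss for the extension, because its baseline must be "on or before first day of extension phase study drug as long as it is within 28 days" of the first extension dose. A late scan does fail that test, but extension efficacy is exploratory and summarized descriptively, so little depends on it.

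Finally, a reader might extend the point to participants who do not roll over, since SAP 4.8.4.1 requires at least one on-treatment scan and SAP 4.4 stops on-treatment efficacy 3 days after the last dose. The documents do not make that a fault. Anyone with an on-treatment Week 24 scan stays in the set, the treatment-policy strategy in SAP 4.3.1.1 is stated for the co-primaries, and an on-treatment MRI set is a choice open to the sponsor.

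**Conclusion.** The gap is real and small, and closing it is a cheap improvement. A direct rollover can be scanned within protocol after open-label drug has started. The SAP then points, without saying so outright, to dropping that scan from the main hippocampal ANCOVA.

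The size is unknown. The documents give neither the number of direct rollovers nor the number of late scans. The extension was added on 24-Apr-2020, so only participants reaching Week 48 after it opened at their site can roll over directly. The 5% case, costing about 2 points of an assumed 80% power, is an illustration. The 15% case needs three quarters of scans to come from direct rollovers and one in five of those to be late; nothing in the documents supports it as an estimate.

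A reader might infer a biased treatment comparison. The documents do not support that. The better reading excludes these scans, both arms roll over to the same drug, and extension dosing starts at 140 mg a day for the first two weeks. On the day-count reading, at most 14 of 350 days (4%) of the interval would be on open-label drug. The co-primary analyses do not depend on the scan.

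**What to change.** In Protocol 8.1.9 and Table 1 footnote 11, add:

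> *For participants entering the Open-Label Extension directly, the Week 48 vMRI is done within 14 days before the Week 48 visit and in any case before the first open-label dose; for all others the window is ±14 days.*

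In SAP 4.8.4.1, add:

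> *Scans taken after the first open-label dose are not used in the main ANCOVA.*

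Check: with the visit on Day 336, the scan falls on Day 322-336. That is inside Day 253-420, inside the double-blind period, and 0 to 14 days before a first open-label dose taken at the visit. One scan then serves both the ANCOVA and the extension baseline.

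The cost is one line in the visit list, one footnote and one SAP sentence, plus tighter scan scheduling for rollovers and occasionally a short delay to the first open-label dose. Scheduling before the visit has a precedent: 8.1.9 already places the sub-study lumbar puncture in the 14 days before Week 48. Sites would need to keep the existing MRI and lumbar puncture sequencing within that fortnight.

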- Participants who early-terminated from the double-blind phase trial or discontinued the study drug for any reason will not be eligible for enrollment in the Open-Label Extension phase.
- All participants must have their Week 48 visit in-person prior to enrolling in the Open-Label Extension phase. (Due to COVID-19, the timing of this visit may be delayed).

All subjects entering the Open-Label Extension phase will start with one capsule of BHV-4157 (140 mg) per day and titrate to two capsules per day after week two (280 mg). This will be done so that all participants will be on open-label medication and will safely continue from either active BHV-4157 or placebo.

All subjects in the Open-Label Extension phase are planned to undergo a termination visit two weeks after the last dose of study drug.

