*NOTE: Participants who have consented to participate in the CSF sub-study will undergo a lumbar puncture for CSF within 14 days prior to this visit. Plasma samples for PK for this subset of participants should be drawn at the time of lumbar puncture. The participant's vitals should be assessed before and after the procedure, or per standard local practice. INR, PT, PTT and platelets should be assessed at the site's local laboratory at least 24 hours, and within normal range, prior to the lumbar puncture. The lumbar puncture should be done after the MRI scan if performed on the same day. If the lumbar puncture is performed on a separate day from the MRI and occurs before the MRI, then there must be at least a 3-day window between the lumbar puncture and the MRI. If the lumbar puncture is performed on a separate day from the MRI and occurs after the MRI, then there is no window (waiting period) between the MRI and lumbar puncture. If a participant in the CSF substudy is terminating early, they do not need to undergo this lumbar puncture. However, every effort will be made to encourage the participant's ongoing voluntary participation and to explain that CSF collection may provide informative information in the future

for the field of AD. Participants will be given an appointment to return in 4 weeks (± 7 days) unless this serves as their Early Termination visit.

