9.4 Sheehan Suicidality Tracking Scale (Sheehan STS)

The Sheehan STS (S-STS) is a prospective, participant self-reported or clinician administered rating scale that contains 16 questions to track both treatment-emergent suicidal ideation and behaviors (Sheehan, Alphs, et al., 2014; Sheehan, Giddens, & Sheehan, 2014). The S-STS will be completed on a paper form at the site. At the screening visit, the recall period for completing the S-STS is 12 months prior; at all other visits, the recall period for completing the S-STS is since the last visit. Subjects who have an S-STS score > 0 should be evaluated by the investigator. If the investigator determines that a subject is at risk of suicide or self-harm, appropriate measures to ensure the subject's safety and obtain mental health evaluation must be implemented. The subject must immediately be discontinued from the study. The event should be recorded as either an AE or SAE as determined by the investigator and reported within 24 hours to the Sponsor.

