The Investigators at each site will make every reasonable effort to maximize participant retention, even if the study treatment is discontinued before week 48. However, if an investigator removes a participant from study, or if a participant declines all further study participation during the study, an Early Termination Visit will be completed as close as possible to the time of study discontinuation. The Early Termination Visit may contain the same assessments as week 48, to allow collection of the main outcome measures. For further detail please refer to the Procedures Manual.

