11.1 Evaluation and Reporting of Adverse Events

All AEs (i.e., a new event or an exacerbation of a pre-existing condition) that occur from the time informed consent is signed and up to 30 days after the study drug has been discontinued must be recorded as an AE on the AE eCRF. The Investigator must follow all AEs until the AE resolves, or until the Investigator and/or the Medical Monitor determine the event is chronic or clinically stable. If an AE remains unresolved at the conclusion of the study, the Investigator and Medical Monitor will make a clinical assessment to determine whether continued follow-up of the AE is warranted. All participants who have received at least one exposure to study therapy will be evaluated for safety of study treatment.

The Investigator should attempt to establish a diagnosis of the event based on signs, symptoms and/or other clinical information. In such cases, the diagnosis should be documented as the AE and not the individual signs/symptoms.

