11.3 Collection and Reporting of Serious Adverse Events

Following written consent to participate in the study, all SAEs, whether related or not related to study drug, must be collected, including those thought to be associated with protocol-specific procedures. The reporting period ends 30 days after discontinuation of dosing. In addition, the investigator should report any SAE occurring after this time period that is believed to be related to study drug or protocol-specific procedures. Serious adverse events that occur prior to initiation of study drug will be documented in the EDC as medical history, but will still need to be reported to on an SAE form as described below.

An SAE is an AE from this study that results in any of the following outcomes:

- Death
- Life-threatening situation (participant is at immediate risk of death)
- Inpatient hospitalization or prolongation of existing hospitalization
- Persistent or significant disability/incapacity
- Congenital anomaly/birth defect in the offspring of a participant who received study drug

Considered significant by the investigator for any other reason

An SAE report should be completed for any event where doubt exists regarding its status of seriousness.

If the investigator believes that an SAE is not related to the study drug, but is potentially related to the conditions of the study (such as a withdrawal of previous therapy or a complication related to study procedure), the relationship should be specified in the narrative section of the SAE Report Form.

SAEs, whether related or not related to study drug, overdose, and potential drug induced liver injury must be reported within 24 hours of the Investigator becoming aware of the event. For this study we will be capturing SAEs through both the ADCS Electronic Data Capture (EDC) system and on an SAE report form provided by CCI In addition, all applicable SAEs must be reported by the Site Investigator to the Institutional Review Board (IRB) of record according to IRB's reporting requirements for such events.

The Site Investigator is responsible for reporting all SAEs and all Other Important Medical Events to via telephone, immediately or no later than 24 hours after awareness of the event. A representative will then immediately notify the Biohaven Medical Monitor. An SAE form must then be submitted to via the fax number indicated below.

Safety Hotline Number for SAE telephone reports:

North America: PPD

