Facsimile (fax) number for SAE report forms, to be sent within 24 hours after awareness of the event:

North America: PPD

The Site Investigator, or designated staff, is also responsible for entering the SAE information in the ADCS Electronic Data Capture (EDC) system (i.e., event term, start stop dates, causality, and severity) according to study-specific eCRF Completion Guidelines. The ADCS Medical Monitor and ADCS Project Director will be automatically notified via email upon entry of an SAE into the ADCS EDC system. A member of the ADCS Medical Safety team will inform the DSMB of the occurrence of any SAEs within 7 days of being reported. The DSMB may at any time request additional information from the ADCS in relation to a reported event.

If only limited information is initially available, follow-up reports are required. If an ongoing SAE changes in its intensity or relationship to study drug or if new information becomes available, a follow-up SAE report should be sent to within 24 hours of the Investigator becoming aware of the updated information using the same procedure used for the transmission of the initial SAE and the same event term should be used. In addition, new or revised event information must be entered into the ADCS EDC at the same time.

All SAEs should be followed to resolution or stabilization. For any questions relating to SAEs, please contact the ADCS Medical Monitor via telephone or email at the number listed on the protocol face page.

Suspected Unexpected Serious Adverse Reactions

Suspected unexpected serious adverse reactions (SUSARs) are serious adverse events that are not listed in the Investigator's Brochure as an expected AE and that the Investigator assesses as possibly related or probably related or definitely related to study drug or study procedure. United States 21 CFR 312.32 and European Union Clinical Trial Directive 2001/20/EC and the associated detailed guidance or national regulatory requirements in participating countries require the reporting of SUSARs to regulatory authorities. As the clinical trial sponsor, Biohaven is responsible for, and has procedures consistent with regulations that will be followed for, expedited reporting of SUSARs.

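### Early Termination visits are exempt from the 4-week return, so leavers who still accept contact have no scheduled check for new adverse events in the rest of the 30-day window

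*Protocol*

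**What the plan says.** - **Return appointment.** Protocol 8.1.9, note: "Participants will be given an appointment to return in 4 weeks (± 7 days) unless this serves as their Early Termination visit".
- **Observation period.** Protocol section 2 provides "a 4-week post-treatment observation period (for subjects who do not participate in the Open-Label Extension phase". The Study Summary and SAP 2.1 state the same 4 weeks with no exception.
- **Access to the extension.** Protocol section 2, repeated in 8.1.12: "Participants who early-terminated from the double-blind phase trial or discontinued the study drug for any reason will not be eligible for enrollment".
- **Who has an Early Termination visit.** Protocol section 10 calls for one "if an investigator removes a participant from study, or if a participant declines all further study participation during the study, an Early Termination Visit", held near the point of exit. Participants who only stop study drug may keep their scheduled visits and are encouraged to do so.
- **Mandatory removal.** Protocol 9.4, for a participant judged at risk of suicide or self-harm: "The subject must immediately be discontinued from the study".
- **Collection window.** Protocol 11.1 has AEs recorded up to 30 days after drug is stopped. Section 11.3 says of SAEs: "The reporting period ends 30 days after discontinuation of dosing". SAP 4.4 counts double-blind AEs to last dose plus 30 days for those who do not enter the extension.
- **Known events.** Protocol 11.1: "The Investigator must follow all AEs until the AE resolves", or is judged chronic or stable. Protocol 11.3: "All SAEs should be followed to resolution or stabilization". Section 11.5 treats clinically significant laboratory results the same way.

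**The concern.** Section 2 and the 8.1.9 note do not agree on whether an early terminator is observed for 4 weeks after treatment. A site following the visit instructions will not book the return, and no other visible provision replaces it.

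The stake is how new events are found. A completer outside the extension gets the Week 52 visit, with AE review, laboratory tests, ECG and the suicidality scale (Protocol 8.1.10). A participant removed from the study close to the last dose gets none of these afterwards. A new AE or SAE inside the plan's own window must still be recorded if the site learns of it, but nobody is scheduled to ask, and the report then depends on a person with dementia or the study partner coming forward. The SAP's treatment-emergent AE tables (4.10.2) and its SAE narratives (4.10.9) both use that 30-day window.

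**Working it through.** **1. The plan's only related figure.** Protocol 12.1.1 assumes at most 26% dropout: 336 × 0.74 = 248.64, stated as 248, so it reproduces. The complement is 336 − 248 = 88. This is a planning bound on missing final data. It does not count Early Termination visits, and it includes people who will refuse contact or who stopped drug well before leaving. It cannot size the affected group.

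**2. Who is owed the 4 weeks.** Section 2 exempts only those entering the extension. Sections 2 and 8.1.12 bar early terminators from the extension, so early terminators fall inside the 4-week period. The 8.1.9 note takes them out. Appendix I Table 1 combines Week 48 and Early Termination in Visit 9 and lists the Week 52 visit as Visit 10, with no exemption shown. Section 8.1.10 places Week 52 after an in-person Week 48 visit, which can be read as a sequencing rule for delayed visits. The inconsistency therefore rests on the 8.1.9 clause.

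**3. Days of the 30-day window with no scheduled contact.** Let d be days from last dose to the last scheduled contact. Uncovered days = max(0, 30 − d).

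| Group | Last scheduled contact | Uncovered days |
|---|---|---|
| Early terminator | d = 0 | 30 |
| Early terminator | d = 7 | 23 |
| Early terminator | d = 14 | 16 |
| Early terminator | d = 30 or later | 0 |
| Extension participant (8.1.12; Table 3) | Day 14 ± 7 | 16 (range 9-23) |
| Completer at Week 52, assuming last dose at the Week 48 visit | Day 28 ± 7 | 2 (range 0-9) |

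The documents do not give d for early terminators, so the first four rows are a range and not an estimate.

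**4. What each remedy leaves for early terminators.**
- Restoring the 4-week visit alone, at its earliest (d + 21): max(0, 30 − (d + 21)) = max(0, 9 − d), which is 9 days at d = 0 and 2 at d = 7. At its nominal time (d + 28) it leaves 2 days at d = 0.
- A call at Day 30-37 after last dose: max(0, 30 − 30) = 0 days.

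**The case against.** The strongest case against is that section 2 is a one-line design description, while 8.1.9 is the operative instruction and makes a deliberate exception. On that view the remedy is a qualifier in section 2. The affected group is also narrow. Section 10's adverse-event criterion stops study medication, not participation, and continued visits are encouraged. People who decline all further participation are owed no appointment. A participant removed for suicide risk under 9.4 must receive safety measures and a mental health evaluation, the event is reported within 24 hours, and it then stays under follow-up. Section 8.1.11 allows unscheduled visits. Section 10 refers to a Procedures Manual, not available here, that could contain a call.

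Most of this stands, and it limits the point to new events in contactable leavers. It does not remove the point: following a known event is not the same as asking about new ones, an unscheduled visit is optional, and the protocol text is inconsistent whatever the manual says.

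Three stronger readings are tempting and are not supported:

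- **That 8.1.9 contradicts the 30-day AE/SAE window.** Sections 11.1 and 11.3 set a recording and reporting duty, and SAP 4.4 an analysis window. None requires a visit at Day 30, and the duty stands without one. This is a gap in ascertainment.
- **That the extension's last visit is a second contradiction.** The two-week visit is stated consistently, and nothing promises extension participants four weeks.
- **That AE counts will be biased between arms.** That would require early exit to differ by arm, which is unknown here. In the 8-week ataxia study in Protocol 1.7.1.1, non-completers were 71 − 64 = 7 of 71 on drug and 70 − 68 = 2 of 70 on placebo (Fisher p = 0.17). That is another disease and 140 mg, and a difference is not established.

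**Conclusion.** The point holds in limited form. The 8.1.9 exemption is inconsistent with the observation period in section 2. As a result, participants who leave within 30 days of last dose and still accept contact have no scheduled enquiry about new AEs or SAEs for up to 30 days, depending on how soon after the last dose the visit falls. Investigator removals, for example under 9.4, are the main group. The number affected is not given.

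The conclusion assumes that the Procedures Manual does not already schedule such a contact. AE analyses are descriptive (SAP 4.10.2), and no efficacy result, power or alpha is affected. This is a low-cost improvement to safety data collection, with medium confidence.

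**What to change.** Amend the 8.1.9 note to say that participants whose Early Termination visit falls within 30 days of last dose, and who agree to contact, receive a safety follow-up consisting at minimum of one AE/SAE telephone call at about Day 30-37 after last dose. Reflect this in 8.1.10 and Appendix I Table 1, with the copy in SAP Appendix 1. A short qualifier in section 2 would then align the design description.

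Do not simply delete the exemption. That would give appointments to people who have declined all participation and to people who stopped drug more than 30 days before leaving, for whom no uncovered days remain.

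The same call may be added for extension participants and for completers last seen before Day 30, as better ascertainment and not as correction of a contradiction.

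The cost is a protocol amendment with IRB approval (Protocol 5.2) and modest site time. Sites already make AE calls at Week 2 (8.1.3) and in the extension (Table 3 footnotes). Some leavers will refuse, and a call yields no laboratory or ECG data.
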